5.1.1.4 Safety Analyses

All safety analyses will be performed on the safety population. All analyses will be based on observed cases without imputation.

5.1.1.4.1 Study Treatment Exposure

Subjects' exposure to the study medication will be characterized by duration of treatment exposure.

Duration of subject exposure to study treatment (days) will be calculated as the study treatment end date minus study treatment start date +1. Duration of treatment exposure will be summarized with descriptive statistics by treatment group.

5.1.1.4.2 Adverse Events

[figure not shown]
An AE is defined as any untoward medical occurrence in a subject administered a pharmaceutical product and that does not necessarily have a causal relationship with this treatment. Adverse events are collected both for the screening/baseline period pretreatment (which are referred to as pretreatment AEs) and for the follow-up period after treatment is initiated (which are referred to as postbaseline AEs). Adverse events will be summarized using the concept of treatment-emergent adverse events (TEAEs). TEAE is a postbaseline AE where:

- a) there is no pretreatment AE of the same MedDRA primary system organ class (SOC) and preferred term (PT); or
- b) the maximum severity during the postbaseline period is greater than the maximal severity of any pretreatment AE of the same MedDRA primary SOC and preferred term during the screening/baseline period; or
- c) the AE reports as a serious AE (SAE) during the postbaseline period

Analysis of the incidence of TEAEs will be performed over the entire study period, and the incidence of TEAEs will be presented and summarized as follows:

- (1) Overall AE, treatment related TEAE, serious AE, deaths, AEs leading to discontinuation and Non-scalp hair growth.
- (2) TEAEs by primary SOC in alphabetical order, PT and severity (maximum severity). The maximum severity of a TEAE experienced by a subject is determined by the greatest severity recorded on the eCRFs for the subject's given TEAE.
- (3) Common (>=2%) TEAEs by Preferred Term
- (4) Treatment related TEAEs by primary SOC in alphabetical order, and preferred term.
- (5) Treatment-emergent serious AEs (SAE) by SOC in alphabetical order, and preferred term.
- (6) TEAEs leading to treatment discontinuation by SOC in alphabetical order, and preferred term
- (7) Treatment-emergent SAE with fatal outcome by primary SOC in alphabetical order, and preferred term. Subject listings will be generated for all AEs, SAE, Deaths, and AEs leading to study discontinuation.

Participant listings will be provided for all AEs, SAEs, AEs leading to study treatment discontinuation, and death (if occurred).

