7.3.3 Safety Analyses

Adverse events will be coded from the verbatim text into preferred term (PT) and primary system organ class (SOC) by using the Medical Dictionary for Regulatory Activities. The number and percent of subjects reporting treatment-emergent AEs at least once regardless of causality will be tabulated. Similarly, treatment-related AEs will be tabulated. The tables will be generated by primary SOC and PT as well as by severity.

[figure not shown]
Safety data will be summarized by frequency distributions or descriptive statistics and described in the detailed analysis plan.

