9.1.3 Severity

A clinical determination will be made of the intensity of an AE. The severity assessment for a clinical AE must be completed using the following definitions as guidelines:

Mild Awareness of sign or symptom, but easily tolerated

Moderate Discomfort enough to cause interference with usual activity

Severe Incapacitating with inability to work or do usual activity

Not applicable In some cases, an AE may be an *all or nothing* finding which cannot be

graded.

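### Tables (4) and (6) of the SAP's adverse event section can miss nonserious on-drug AEs that were judged related or ended treatment, because both count only TEAEs

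*SAP*

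**What the plan says.** SAP 5.1.1.4.2 separates pretreatment AEs from postbaseline AEs and makes a postbaseline AE a TEAE under any one of three clauses:

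- (a) "there is no pretreatment AE of the same MedDRA primary system organ class (SOC) and preferred term (PT");
- (b) "the maximum severity during the postbaseline period is greater than the maximal severity of any pretreatment AE of the same MedDRA primary SOC", matched on preferred term as well;
- (c) "the AE reports as a serious AE (SAE) during the postbaseline period".

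The two tables at issue use that definition. Table (4) is "Treatment related TEAEs by primary SOC in alphabetical order, and preferred term". Table (6) is "TEAEs leading to treatment discontinuation by SOC in alphabetical order, and preferred term". The overview in item (1) is worded differently: "Overall AE, treatment related TEAE, serious AE, deaths, AEs leading to discontinuation and Non-scalp hair growth".

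Protocol 7.3.3 tabulates treatment-emergent AEs whatever their causality and then says "Similarly, treatment-related AEs will be tabulated". Protocol 9.1.1 collects AEs from informed consent. Protocol 9.1.3 grades severity as mild, moderate or severe and also allows an ungraded category. SAP 5.1.1.4.2 provides subject listings of all AEs and of all AEs leading to treatment discontinuation.

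**The concern.** None of the three clauses asks whether the on-drug event is a new episode, whether the investigator thought it related, or whether it stopped treatment. For a nonserious AE whose term was already recorded in screening, only an increase in severity counts. An event can therefore be the recorded reason for stopping study drug and still be absent from the table of events that stopped study drug.

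The trial's first hypothesis (Protocol 2.2) is an acceptable safety profile, and these descriptive tables are part of the evidence for it. With about 80 and 72 subjects, related events and discontinuations may number only a few, so each subject counts. The listings keep the events but do not give rates by arm and preferred term.

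**Working it through.** The plan states no figure on this point, so there is nothing to reproduce. The check has three steps: apply the definition case by case, trace one subject through the outputs, and show an illustrative size.

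**Step 1. Apply (a) to (c).** Inputs are the clauses in SAP 5.1.1.4.2 and the order mild < moderate < severe from Protocol 9.1.3. For a nonserious postbaseline AE:

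| Pretreatment AE, same SOC and PT | Postbaseline maximum mild | Moderate | Severe |
|---|---|---|---|
| None | TEAE by (a) | TEAE by (a) | TEAE by (a) |
| Mild | not a TEAE | TEAE by (b) | TEAE by (b) |
| Moderate | not a TEAE | not a TEAE | TEAE by (b) |
| Severe | not a TEAE | not a TEAE | not a TEAE |

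With a pretreatment match there are 3 × 3 = 9 pairings. Kept: 2 + 1 + 0 = 3. Dropped: 1 + 2 + 3 = 6. If the postbaseline AE is serious, all 9 are kept by (c). Causality, action taken and new onset change no cell. These are counts of cells, not probabilities.

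**Step 2. Trace one hypothetical subject.** He has a mild headache in screening that resolves. On drug he has mild headaches, judged related and nonserious, and treatment is stopped for them.

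- Clause (a) fails, because the term was recorded before treatment.
- Clause (b) fails, because mild is not greater than mild.
- Clause (c) fails, because the event is nonserious.
- He has no TEAE for headache, so the event is in neither table (4) nor table (6). It is in the listings.

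**Step 3. Illustrative size.** The planned arm sizes (SAP 4.1) are 80 and 72, so one subject is 1/80 = 1.25% or 1/72 = 1.39%. Let f be the share of subjects with a nonserious postbaseline AE that is related or ends treatment and is dropped by the rule. The documents give no value for f, so the range below is an assumption. Expected number omitted = n × f; chance of at least one = 1 − (1 − f)^n.

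| f (assumed) | n = 80: expected | n = 80: at least one | n = 72: expected | n = 72: at least one |
|---|---|---|---|---|
| 0.5% | 0.40 | 33.0% | 0.36 | 30.3% |
| 1% | 0.80 | 55.2% | 0.72 | 51.5% |
| 2% | 1.60 | 80.1% | 1.44 | 76.7% |
| 5% | 4.00 | 98.3% | 3.60 | 97.5% |

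The result depends entirely on f.

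**The case against.** The case against acting is that the effect is narrow and much of the information survives elsewhere. The following stands:

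- The trigger is only an AE recorded between consent and first dose. Conditions before the Screening Visit are medical history (SAP 5.1.1.2.5) and trigger nothing.
- Clause (b) uses the subject's postbaseline maximum for the term, so one worse episode appears to bring in the milder ones.
- SAP 5.1.1.2.1 summarizes exits by arm, with AEs as a named reason and no TEAE filter. That covers part of the loss. It counts study exits rather than treatment stops and gives no preferred term. It also uses the mITT population (SAP 5.1.1.2), which leaves out a subject with no postbaseline coprimary measurement.

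A reader might also infer more than the documents support:

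- *That all recurring on-drug AEs are lost.* Clause (c) keeps every serious one and clause (b) every one that worsens.
- *That the SAP contradicts Protocol 7.3.3.* The protocol sentence "Similarly, treatment-related AEs will be tabulated" directly follows one on treatment-emergent AEs, and its opening word can carry that scope forward. The wording differs, but a conflict is not established.
- *That the overview omits these subjects too.* Item (1) speaks of AEs, not TEAEs, for discontinuation, under a lead-in about TEAE incidence. It is ambiguous.
- *That terms will drop out of the common-AE table.* The SAP does not say whether its 2% cut is per arm or pooled, and no rates are given.
- *That an ungraded AE with a pretreatment match can never be a TEAE unless serious.* The visible SAP gives no ranking for that category, and table specifications are in a separate document (SAP 4).
- *That the comparison is biased.* The same rule applies to both arms, and no direction can be derived.

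**Conclusion.** As written, SAP 5.1.1.4.2 excludes from TEAE status a nonserious postbaseline AE whose SOC and preferred term were recorded before treatment at equal or greater severity. Causality, new onset and action taken make no difference. Tables (4) and (6) can therefore undercount related AEs and AEs leading to treatment discontinuation. This follows from the text and needs no assumption.

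The size cannot be derived. It depends on how often screening AEs recur on drug without worsening, which the documents do not report, and it may be zero or one subject per arm. No efficacy result is affected and no between-arm bias is shown. The point is a cheap improvement to safety reporting, not a defect that threatens the trial's conclusions.

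**What to change.** In SAP 5.1.1.4.2, leave the TEAE definition and the general TEAE tables as they are, and make three changes before database lock:

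1. Build table (4) on all postbaseline AEs judged treatment-related, regardless of TEAE status.
2. Build table (6) on all postbaseline AEs leading to treatment discontinuation, regardless of TEAE status.
3. Word the related and discontinuation rows of item (1) to match.

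Widening the TEAE definition itself is less attractive. A clause based on causality would make emergence depend on the investigator's judgment. A clause based on resolution of the earlier episode would depend on stop dates, which SAP 6.3 imputes to month end or 31 December when partial.

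The cost is a few words in the SAP and a changed selection in two tables and the overview. Relationship and action taken are already collected (Protocol 6.3.1), so no new data are needed. Counts in tables (4) and (6) may rise slightly in either arm. These tables will also no longer nest strictly within the TEAE table, which a footnote should state.

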2.2 Clinical Hypotheses

- Setipiprant tablets 1000 mg BID have an acceptable safety profile following oral administration for 24 weeks.
- Setipiprant tablets 1000 mg BID are more effective than placebo in increasing hair growth, as measured by the change from baseline in target area hair count (TAHC) of terminal hairs (1 cm² circular area) using digital image analysis at 24 weeks after oral administration.
- Setipiprant tablets 1000 mg BID are more effective than placebo in increasing scalp hair growth, as measured by the distribution of Subject Self-Assessment (SSA) scores using a 7-point scale at 24 weeks after oral administration.

3. Study Design

[figure not shown]
This is a multicenter, randomized, double-blind, placebo-controlled study with an active comparator group designed to determine the effect of treatment with setipiprant tablets 1000 mg BID on scalp hair growth as assessed by objective (ie, imaging-based) and subjective (ie, investigator- and subject-reported) measures.

All investigators, site staff, and subjects will be blinded to whether subjects receive setipiprant or matching placebo during the study.

Subjects must complete all screening and baseline procedures and meet all eligibility requirements to qualify for enrollment and randomization on Day 1 when they will be randomly

assigned to 1 of 2 treatment groups (setipiprant or placebo). All subjects will self-administer the assigned study drug over a 24 week period to evaluate the safety and effects on hair growth. After randomization, subjects will return to the research facility at Weeks 24 for protocol-defined efficacy and/or safety assessments and procedures, confirmation of compliance with study drug usage, and new study drug dispensation (except for Week 24). A follow-up visit will occur at Week 32 (ie, 8 weeks posttreatment) or the early exit visit for protocol-defined efficacy and safety evaluations and procedures.

Safety and efficacy assessments and study procedures are outlined in the Study Design and Schedule of Assessments (Table 1). The SSA will be evaluated at Weeks 24, and 32 (or early exit visit) using the subject's paired and randomly blinded screening (the screening photograph is defined as the subject's baseline) and postbaseline photographs, and at Weeks 24 and 32 (or early exit visit) using the subject's paired, unblinded screening and postbaseline photographs.

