9.1 Definitions

9.1.1 Adverse Event

An AE is any untoward medical occurrence in a patient or clinical investigation subject administered a pharmaceutical product and that does not necessarily have a causal relationship with this treatment. An AE can therefore be any unfavorable and unintended sign (including an abnormal laboratory finding), symptom, or disease temporally associated with the use of a medicinal (investigational) product, whether or not related to the medicinal (investigational) product. In addition, during the screening period, AEs will be assessed regardless of the administration of a pharmaceutical product.

Note: Adverse events must be collected once informed consent has been obtained, regardless of whether or not the subject has been administered study drug.

Progression of treatment indication including new or worsening of anticipated clinical signs or symptoms, which are collected as clinical efficacy variables and assessed as unequivocally associated with the disease progression and/or lack of efficacy, should NOT be reported as AEs unless the disease progression is greater than anticipated in the natural course of the disease.

Adverse events will be assessed, documented, and recorded in the CRF throughout the study (ie, after informed consent has been obtained).

. All reported AEs will be documented on the appropriate case report form.

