6.1.1 Analysis Days

- Study days will be calculated as visit date baseline date (day 1) + 1 if visit date is on or after baseline date; otherwise it will be calculated as visit date -baseline date (day 1).
- Treatment period is defined as days between the date of study treatment start and the date of the study treatment end.

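### The TEAE tables pool 24 weeks on drug with 8 weeks off drug, and no visible summary separates the two

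*SAP*

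**What the plan says.** SAP 5.1.1.4.2 divides AEs into pretreatment and postbaseline. Postbaseline begins when treatment starts, and no end is given. A postbaseline AE is a TEAE if its term was not reported before treatment, if it is more severe than before treatment, or if it is serious. On the window, the section says: "Analysis of the incidence of TEAEs will be performed over the entire study period". Seven TEAE summaries follow, and none is divided into on-treatment and posttreatment.

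The study continues past the last dose. Protocol 3 gives 24 weeks of dosing and then: "A follow-up visit will occur at Week 32 (ie, 8 weeks posttreatment) or the early exit visit". Protocol 9.1.1 collects events for as long: "Adverse events will be assessed, documented, and recorded in the CRF throughout the study".

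The safety hypothesis in Protocol 2.2 is that setipiprant tablets "have an acceptable safety profile following oral administration for 24 weeks". SAP 6.1.1 already has the concept needed to match that wording: "Treatment period is defined as days between the date of study treatment start and the date of the study treatment end". The TEAE rule does not use it.

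**The concern.** An AE that first appears in Week 31, in a subject whose last dose was at Week 24, is tabulated as treatment-emergent beside events that arose on drug. A reader who wants tolerability during 24 weeks of dosing cannot get it from the planned tables without rebuilding it from the listings.

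Elsewhere the plan keeps the periods apart:

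- Exposure is summarised to treatment end only (SAP 5.1.1.4.1), so the exposure and AE tables cover different windows.
- Disposition is reported at Week 24 and again at study end (SAP 5.1.1.2.1).
- Week 32 efficacy is handled separately from Week 24, without imputation (SAP 6.5).
- The blinded safety review covers the 24-week treatment period (Protocol 3.2).

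AEs are the visible exception, in a trial whose single objective names safety and tolerability. At stake is how the descriptive comparison of the two arms is read.

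**Working it through.** **Window.** 32 − 24 = 8 weeks off drug, and 8/32 = 25% of a completer's postbaseline time. The share can be larger for someone who stops drug early and still returns at Week 32, which Protocol 5.3 allows after unblinding. It can be smaller for someone who leaves at an early exit visit.

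**Inputs.** The documents give no AE rates, so the 24-week incidences below are assumptions: *p* for placebo and *s* for setipiprant. I also assume a constant hazard within each period, full follow-up, and an off-drug hazard equal to the placebo hazard in both arms. Eight weeks is one third of 24, so:

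- placebo over 32 weeks: 1 − (1 − p)(1 − p)^(1/3)
- setipiprant over 32 weeks: 1 − (1 − s)(1 − p)^(1/3)

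Subtracting gives a 32-week risk difference of (s − p)(1 − p)^(1/3). The difference therefore shrinks only by the factor (1 − p)^(1/3), which is close to 1 when events are uncommon.

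Example, 10% vs 20%: 0.90^(1/3) = 0.9655. Placebo is 1 − 0.90 × 0.9655 = 13.1%, and setipiprant is 1 − 0.80 × 0.9655 = 22.8%. The ratio falls from 2.00 to 1.74, and the difference from 10.0 to 9.7 points.

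| 24-week placebo vs setipiprant (assumed) | 32-week | Ratio, 24 → 32 weeks | Difference in points, 24 → 32 weeks |
|---|---|---|---|
| 2% vs 4% | 2.7% vs 4.6% | 2.00 → 1.75 | 2.0 → 1.99 |
| 5% vs 10% | 6.6% vs 11.5% | 2.00 → 1.74 | 5.0 → 4.9 |
| 5% vs 12% | 6.6% vs 13.5% | 2.40 → 2.04 | 7.0 → 6.9 |
| 10% vs 20% | 13.1% vs 22.8% | 2.00 → 1.74 | 10.0 → 9.7 |
| 20% vs 40% | 25.7% vs 44.3% | 2.00 → 1.72 | 20.0 → 18.6 |
| 40% vs 60% | 49.4% vs 66.3% | 1.50 → 1.34 | 20.0 → 16.9 |
| 50% vs 60% | 60.3% vs 68.3% | 1.20 → 1.13 | 10.0 → 7.9 |

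In the rows with a true ratio of 2.0, subjects whose first event falls off drug make up about 22–25% of placebo subjects with the event and 10–14% of setipiprant subjects. With no drug effect, both windows give a ratio of 1.0.

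**Dependence on the off-drug assumption**, at 10% vs 20%:

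- If the setipiprant hazard stays at its on-drug level for the 8 weeks, its 32-week incidence is 1 − 0.80^(4/3) = 25.7%. The ratio is 25.7/13.1 = 1.96, and the difference rises to 12.6 points.
- If there is no effect on drug (10% vs 10%) but the hazard doubles after stopping, setipiprant reaches 1 − 0.90 × 0.90^(2/3) = 16.1%. The pooled ratio is 16.1/13.1 = 1.23, although the on-drug ratio is 1.0.

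**A planned table that can change.** Summary (3) in SAP 5.1.1.4.2 lists terms at 2% or more. If the safety population matches the planned 80 and 72, one subject is 1/80 = 1.25% or 1/72 = 1.39%, and two are 2.5% or 2.8%. One off-drug event can bring a preferred term into that table.

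**The case against.** The strongest reply is that whole-study counting is an open and inclusive choice. It matches collection throughout the study, and Week 32 is itself a safety visit. The objective in Protocol 2.1 sets no 24-week limit. Treatment-related TEAEs are tabulated separately, which filters some background events. TEAEs leading to treatment discontinuation are largely unaffected, because they must precede stopping. All AEs are listed. This stands as a reason to keep the whole-study tables, but not as a reason to have only those.

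A reader might infer that the window weakens a formal test of the 24-week safety hypothesis. The documents do not support that. The hypothesis is qualitative, with no margin or threshold. The null and alternative hypotheses in Protocol 7.3.1 cover only TAHC and SSA, and Protocol 7.3.3 makes safety descriptive. No type I error, power or decision rule is involved.

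A reader might also infer that the window makes setipiprant look safer. That needs its hazard to fall to the placebo level straight after the last dose, which the documents do not say. The two alternative cases in the working show a larger difference or a spurious on-drug signal instead. Absolute percentages rise in both arms in any case. Nor should ratios alone be cited, since the differences for uncommon events hardly change.

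Replacing the whole-study table with a cut at the last dose would bring its own problem. If one arm stops drug earlier, its counted time is shorter and its crude incidence falls.

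Finally, parts of the safety text are blacked out and the table specifications sit in a separate document, so a split by period may exist there. The visible list of seven summaries contains none.

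**Conclusion.** The point holds as a modest reporting gap in a descriptive safety analysis. For completers, a quarter of the time that feeds the TEAE tables is off drug, and the visible plan offers no way to see the 24 treated weeks alone.

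If the setipiprant hazard returns to the placebo level after the last dose, a true ratio of 2.0 reads as about 1.72 to 1.75, a loss of 13–14%. Risk differences shrink by about 1–7% for placebo incidences up to 20%, and by more for commoner events. These sizes rest on assumed incidences, constant hazards and complete follow-up. If effects are delayed or follow withdrawal, the direction changes, and the pooled table cannot show which case applies. That ambiguity is the main argument for a split, whichever way the bias runs.

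**What to change.** In SAP 5.1.1.4.2, before unblinding:

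1. Keep the whole-study TEAE tables and label them as covering treatment plus follow-up.
2. Add a TEAE summary by arm limited to the treatment period of SAP 6.1.1, plus any lag fixed in advance. Show exposure time alongside, so that unequal stopping is visible.
3. Add a separate by-arm table of AEs with onset or worsening after that point.
4. Keep SAEs and deaths on a whole-study basis.

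No new data are needed. Onset dates are collected (Protocol 6.3.1), and imputation rules already exist for treatment end (SAP 6.1.2) and for partial AE dates (SAP 6.3).

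The cost is a few extra tables and one assignment rule for partial dates near the last dose. SAP 6.3 sets a missing onset day to the first of the month, which would tend to place such events on treatment. It also restricts what imputed dates may be used for, so its wording must be extended to cover the split. Two limitations remain: subjects who stop early have less counted time in the on-treatment table, and a delayed drug effect would appear in the posttreatment table, so the two should be read together.
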